9.3.2. Primary Endpoint Analysis

PK/PD model will be established to characterize the relationship between sisunatovir plasma concentration and change from baseline in Fridericia's heart-rate corrected QT interval ($\Delta QTcF$) using the concentration-QTc analysis set. Based on the recommendation in the White Paper¹¹, the linear mixed effect model preferred is pre-specified as:

$$\Delta QTcF_{ijk} = \theta_0 + \eta_{0,i} + \theta_1 TRT_j + (\theta_2 + \eta_{1,i}) C_{ijk} + \theta_3 TIME_j + \theta_4 (QTc_{ij0} - \bar{QTc}_0) + \varepsilon_{ijk}$$

$\Delta QTcF_{ijk}$ is the change from baseline in QTcF for participant i in treatment j at time k; θ_0 is the population mean intercept in the absence of a treatment effect; $\eta_{0,i}$ is the random effect associated with the intercept term θ_0 ; θ_1 is the fixed effect associated with treatment TRT_j (0 = placebo, 1 = sisunatovir); θ_2 is the population mean slope of the assumed linear association between plasma sisunatovir concentration and $\Delta QTcF_{ijk}$; $\eta_{1,i}$ is the random effect associated with the slope θ_2 ; C_{ijk} is the plasma concentration of sisunatovir for participant i in treatment j and time k and $C_{ijk} = 0$ for placebo group; θ_3 is the fixed effect associated with time; and θ_4 is the fixed effect associated with centered baseline QTc_{ij0} , where \bar{QTc}_0 is overall mean of QTc_{ij0} , i.e., the mean of all the baseline (= time 0) QTcF values. It is assumed the random effects ($\eta_{0,i}$, $\eta_{1,i}$) are normally distributed with mean [0,0] and an unstructured covariance matrix, whereas the residuals ε_{ijk} are normally distributed with mean 0 and variance σ^2 .

The model-derived mean $\Delta\Delta QTcF$ and corresponding two-sided 90% CIs will be computed at concentrations of interests eg, expected C_{max} at the **CCI**. If the upper bound of the two-sided 90% interval for the $\Delta\Delta QTcF$ as estimated by the final concentration-QTc model established in this study is < 10 msec at the highest clinically relevant exposure, the absence of an effect of sisunatovir on QTc will be concluded. The highest clinically relevant exposure (due to intrinsic and/or extrinsic factors) will be determined later from other studies.

Details of the modelling approach including the structural model, assumptions, criteria for model selection and evaluation as well as potential changes to the pre-specified model, if needed based on constraints of the available data, will be described in the SAP.

The modeling output will be reported as stand-alone report or within specific sections in the clinical study report. The information to be reported will be outlined in the SAP.

9.3.3. Secondary Endpoints Analysis

Change from baseline in QTcF intervals will be analyzed using a MMRM model with sequence, period, treatment, time (post-dose timepoint) and treatment by time interaction as fixed effects, participants as a random effect, and baseline QTcF as the covariate. A compound symmetry covariance matrix will be fitted to the repeated times within participant (other covariance matrices will be considered if necessary), and the Kenward-Roger approximation will be used for estimating degrees of freedom. The ECG analysis set will be

used for the MMRM analysis. The lower limit of the Bonferroni-adjusted 90% CI (96.7% CI) of mean difference of moxifloxacin over placebo at 3, 4, and 5-hr post-dose will be reported separately and compared to the threshold of 5 msec.

See Section 9.3.4 for the secondary endpoints of safety analyses.

9.3.4. Safety analyses

All safety analyses will be performed on the Safety Analysis Set as defined in Section 9.2.

AEs, ECGs, BP, heart rate, continuous cardiac monitoring, and safety laboratory data, as applicable, will be reviewed and summarized on an ongoing basis during the study to evaluate the safety of participants. Any clinical laboratory, ECG, BP, and heart rate abnormalities of potential clinical concern will be described. Safety data will be presented in tabular and/or graphical format and summarized descriptively, where appropriate.

Medical history and PE information, as applicable, collected during the course of the study, will be considered source data and will not be required to be reported, unless otherwise noted. However, any untoward findings identified on physical conducted during the active collection period will be captured as AEs, if those findings meet the definition of an AE. Data collected at screening that are used for inclusion/exclusion criteria, such as laboratory data, ECGs, and vital signs, will be considered source data, and will not be required to be reported, unless otherwise noted. Demographic data collected at screening will be reported.

The number (%) of participants with maximum postdose QTcF values and maximum increases from baseline in the following categories will be tabulated by treatment:

Safety QTcF Assessment

Degree of Prolongation	Mild (ms)	Moderate (ms)	Severe (ms)
Absolute value	>450-480	>480-500	>500
Increase from baseline		30-60	>60

9.3.5. Exploratory Endpoints Analysis

Details on the analyses of Exploratory endpoints will be described in the SAP.

9.4. Interim Analyses

No interim analysis will be conducted for this study. As this is a sponsor-open study, the sponsor may conduct unblinded reviews of the data during the course of the study for the purpose of safety assessment, facilitating PK/PD modeling, and/or supporting clinical development.

9.5. Sample Size Determination

A sample size of 42 (7 per sequence) participants will provide approximately 99% power to detect a 5 msec difference between moxifloxacin and placebo at historical moxifloxacin

Tmax (3 hour) to demonstrate the study sensitivity, if the expected mean difference between moxifloxacin and placebo is no less than 10 msec at Tmax.

This calculation used a 1-sided 5% paired t-test and assumed a conservative estimate of common intra-subject standard deviation of 5.61 msec for the change from baseline in QTcF, based on a previous study (C5241001). Previous PCRU TQT studies (A4301023, A3921028, A5761016, A5951151, A5271032, A4251025, A7691017 and B1811062) had an average dropout rate of approximately 2%. Assuming a 2% dropout rate, 41 participants would provide approximately 99% power to demonstrate the study sensitivity.

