participants who meet the entry criteria will be admitted on Day -1, prior to treatment administration on Day 1, and will reside in the PCRU until completion of protocol assessments on Day 4. Participants may be discharged between study periods at the discretion of the investigator. There will be a washout of at least 7 days between dose administrations in consecutive crossover treatment periods. Follow-up contact will be made at least 28 calendar days and up to 35 calendar days after the last administration of the investigational product to capture any potential AEs and concomitant treatments, and to confirm appropriate contraception usage, contact with the participant may be done via phone. For each participant, the duration of participation from Period 1 admission to discharge will be approximately 4 weeks. The follow-up call will occur up to 5 weeks after last dose of study drug .

Study Intervention(s)			
Intervention Name	PF-07923568 (sisunatovir)	Placebo for PF-07923568 (sisunatovir)	Moxifloxacin
Treatment Arm	A	B	C
Unit Dose Strength(s)	50 mg	Placebo	400 mg
Dose Formulation	Capsule	Capsule	Tablet
Dosage Level(s)	Planned doses are CCI* mg CCI for CCI doses	0 mg CCI for CCI doses	400 mg moxifloxacin on Day CCI**
Route of Administration	Oral	Oral	Oral
Use	Experimental	Placebo-comparator	Active-comparator
IMP or NIMP/AxMP	IMP	IMP	AxMP

* Dose will be adjusted to the highest feasible dose that is sufficient well tolerated, up to CCI .

** Sisunatovir placebo will be administered CCI for CCI doses, followed by a single dose of 400 mg moxifloxacin on Day CCI .

Statistical Methods:

In this study approximately 42 participants will be enrolled. Statistical power analyses suggest that 42 participants will provide approximately 99% power to detect a mean difference of 5 msec between moxifloxacin and placebo at 3 hours post-dose of moxifloxacin (historic population T_{max}) if the expected mean difference between moxifloxacin and placebo is no less than 10 msec at T_{max} .

For the primary objective, a PK/pharmacodynamic (PD) model will be established to characterize the relationship between sisunatovir plasma concentration and change from baseline in heart rate-corrected QT interval (ΔQTc) in this study. Change from baseline in Fridericia's heart-rate corrected QT interval ($\Delta QTcF$) will be the default dependent variable.

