The model-derived mean placebo-corrected change from baseline in QTc ($\Delta\Delta QTcF$) and corresponding 2-sided 90% confidence intervals (CIs) will be computed at concentrations of interests, eg, expected C_{max} at the CCI [REDACTED]. If the upper bound of the 2-sided 90% interval for the $\Delta\Delta QTcF$ as estimated by the final concentration- ΔQTc model established in this study is <10 msec at the highest clinically relevant exposure, the absence of an effect of sisunatovir on QTc will be concluded. The highest clinically relevant exposure (due to intrinsic and/or extrinsic factors) will be determined later from other studies.

For the secondary objective to determine study sensitivity, the change from baseline QTcF interval will be analyzed using a MMRM model with sequence, period, treatment, time (post-dose timepoint), and treatment by time interaction as fixed effects, participants as random effect, and baseline QTcF as covariate. Estimates of the mean difference between moxifloxacin and placebo at 3, 4, and 5 hrs post-dose and the corresponding two-sided Bonferroni-adjusted 90% CIs (96.7% CIs) will be reported separately. This study will be deemed sensitive to detect QT/QTc prolongation if the lower limit of the Bonferroni-adjusted 90% CI (96.7% CI) of mean difference between moxifloxacin and placebo at any of the 3, 4, or 5 hrs post-dose is greater than 5 msec.

[figure not shown]
Ethical Considerations:

There is no known benefit for healthy participants participating in this trial. This study is designed primarily to investigate the effects of sisunatovir on QTc Interval.

Based on the data from completed Phase 1 and 2 studies, the clinical safety profile of sisunatovir appears to be acceptable. Sisunatovir will be administered in this study at doses that were found to be well tolerated in previous studies.

Moxifloxacin is a fluoroquinolone antibiotic that produces consistent and predictable QT prolongation and a single dose of 400 mg is routinely used as a positive control in Concentration QT/QTc (C-QT) studies.

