3. OBJECTIVES AND ENDPOINTS

Objectives	Endpoints
Primary:	Primary:

To evaluate the effect on QT interval corrected for heart rate (QTc) interval in healthy participants, of possible clinical therapeutic concentrations of sisunatovir compared with placebo.	
Placebo-corrected, baseline adjusted QTc interval using Fridericia's correction method (QTcF) of sisunatovir at expected maximum concentrations (C_{max}) at the CCI [REDACTED].
Secondary:	Secondary:

To evaluate the safety and tolerability at possible clinical therapeutic concentrations of sisunatovir, including but not limited to cardiovascular safety.To determine study sensitivity by comparing the effect of moxifloxacin 400 mg on QTc interval with placebo at historical moxifloxacin time for maximum observed concentration (T_{max}) of 3-5 hours.	
Adverse event (AE), ECG assessments, vital sign measurements, and clinical safety laboratory measurements.Baseline adjusted QTcF of moxifloxacin and placebo at T_{max} of 3, 4, and 5 hours on Day 3.
Exploratory:	Exploratory:

To evaluate the effect of sisunatovir on the electrocardiogram (ECG) parameters of, heart rate, PR interval and QRS interval.To evaluate the plasma pharmacokinetics (PK) of sisunatovir following multiple oral doses.To explore PK of sisunatovir by microsampling technique.	
Baseline adjusted heart rate, PR interval, and QRS intervals of sisunatovir and placebo at each postdose time point.Plasma sisunatovir parameters, including C_{max}, T_{max} and area under the plasma concentration-time profile from time 0 to 24 hours (AUC₂₄) post-dose on Day 3.Concentration of sisunatovir from paired samples obtained via microsampling compared to venous sampling.

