9.1.2. Assay Sensitivity

The assay sensitivity is tested at 3, 4 and 5-hours post-dose of positive control, moxifloxacin, on Day 3 simultaneously at one-sided $\alpha = 0.05$ level with Bonferroni correction of $\alpha/3$ for multiple assessments. Denote the population mean of change from baseline in QTcF of moxifloxacin and placebo at 3, 4, or 5-hr post-dose as $\mu(M)$ and $\mu(P)$, respectively, the statistical hypotheses are:

$$H_0: \mu(M) - \mu(P) \leq 5 \text{ msec}$$

$$H_a: \mu(M) - \mu(P) > 5 \text{ msec}$$

The study will be deemed adequately sensitive to detect QT/QTc prolongation if any of the lower limits of the two-sided Bonferroni-adjusted 90% CI (96.7% CI) for mean differences between moxifloxacin and placebo at any of the 3, 4 and 5-hr post-dose, respectively, are greater than 5 msec.

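### The stated 99% power is for one unadjusted one-sided 5% test at 3 hours, but assay sensitivity is decided at 3, 4 and 5 hours at alpha/3 with success at any one hour

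*Protocol*

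**What the plan says.** **The sizing.** Protocol 9.5 randomizes 42 participants and claims about 99% power for moxifloxacin against placebo at "Tmax (3 hour) to demonstrate the study sensitivity", provided the true difference is at least 10 msec. The basis is given as follows: "This calculation used a 1-sided 5% paired t-test and assumed a conservative estimate of common intra-subject standard deviation of 5.61 msec". After 2% dropout, it says "41 participants would provide approximately 99% power to demonstrate the study sensitivity". The synopsis makes the same single-hour claim: "approximately 99% power to detect a mean difference of 5 msec between moxifloxacin and placebo at 3 hours post-dose of moxifloxacin".

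**The decision rule.** Protocol 9.1.2 tests 3, 4 and 5 hours on Day 3 "with Bonferroni correction of $\alpha/3$ for multiple assessments". It declares the study sensitive "if any of the lower limits of the two-sided Bonferroni-adjusted 90% CI (96.7% CI) for mean differences between moxifloxacin and placebo" exceed 5 msec at any of those hours. SAP 5.1.2 and 6.2.2 repeat the rule. Protocol 9.3.3 uses the same adjusted interval and threshold, and SAP Appendix 2 codes a two-sided alpha of 0.033. The synopsis also carries this version, requiring that the lower limit for the "mean difference between moxifloxacin and placebo at any of the 3, 4, or 5 hrs post-dose is greater than 5 msec".

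**The Tmax label.** Section 9.5 treats historical Tmax as 3 hours. The objective in Protocol 3 refers to the "historical moxifloxacin time for maximum observed concentration (T_{max}) of 3-5 hours".

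**The concern.** A power statement should describe the test that decides the question. This one uses a different alpha (0.05 instead of 0.05/3) and a different number of tests (one instead of three), and it does not reflect the any-one-hour success rule. The synopsis contains both versions, a few paragraphs apart. Section 9.5 is the only sample-size justification in either document, and it does not give a reader the power of the rule that will be used.

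The two differences pull in opposite directions. The stricter alpha lowers power at each hour, and three chances to succeed raise it. The net effect therefore has to be calculated.

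The 3-hour label adds a smaller mismatch. Protocol 4.2 says that food delays moxifloxacin's peak QTc effect to 4 hours, and this study doses in the fed state. Correcting the label changes no number.

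**Working it through.** **Inputs.** All are from Protocol 9.5 except the threshold and adjusted alpha, which are in 9.1.2.
- True difference 10 msec and threshold 5 msec, so the margin tested is 10 - 5 = 5 msec.
- Intra-subject SD 5.61 msec, so the SD of a paired difference is 5.61 × √2 = 7.93 msec.
- n = 42, or 41 after dropout.
- Alpha (one-sided): 0.05 as sized; 0.05/3 = 0.01667 as decided; 0.033/2 = 0.0165 as coded in SAP Appendix 2.

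**Method for one hour.** Noncentral t with df = n - 1 and ncp = 5 / (7.934/√n):
- n = 42: standard error 7.934/√42 = 1.224, ncp = 5/1.224 = 4.08.
- n = 41: standard error 7.934/√41 = 1.239, ncp = 5/1.239 = 4.04.

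**Step 1: reproduce the plan's figure, then change only alpha.**

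| One-sided alpha | Critical t (n=42 / n=41) | Power, n=42 | Power, n=41 |
|---|---|---|---|
| 0.05 (as sized) | 1.683 / 1.684 | 99.1% | 99.0% |
| 0.05/3 (as decided) | 2.202 / 2.204 | 96.7% | 96.3% |
| 0.0165 (SAP code) | 2.207 / 2.209 | 96.7% | 96.3% |

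The 99% is right for the test named in 9.5. Reading 5.61 as the SD of the difference itself would give more than 99.99%, so 5.61 × √2 is the reading behind the plan's figure.

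A normal-approximation check at 0.05/3 uses Φ(ncp - 2.128). It gives 97.5% (n=42) and 97.2% (n=41), so the t degrees of freedom account for less than 1 point.

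**Step 2: the any-of-three rule.** This needs the correlation between hours and an expected effect at each hour. The documents give neither. Assumption: a common correlation of 0.3, 0.5 or 0.8. For each setting, 200,000 trials were simulated with three correlated paired differences of SD 7.934 per participant. Each hour was tested against 5 msec at one-sided 0.05/3, and a trial succeeded if any hour rejected.

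| True difference at the three hours (msec) | n=42 | n=41 |
|---|---|---|
| One hour at 10, the other two at 0 or 5 | 96.7% to 96.8% | 96.3% to 96.4% |
| 10 at all three, correlation 0.3 | 99.9% | 99.9% |
| 10 at all three, correlation 0.5 | 99.8% | 99.7% |
| 10 at all three, correlation 0.8 | 99.0% | 98.9% |

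**Step 3: difference from the sized test at the same n.** The largest loss is 96.3 - 99.0 = -2.7 points (n=41, one effective hour). The largest gain is 99.92 - 98.99 = +0.9 points (n=41, all hours at 10 msec, correlation 0.3).

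These are paired t-test figures, the plan's own sizing method. They are not the power of the planned MMRM, whose standard error may differ.

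**The case against.** The strongest reply is that nothing in 9.5 is false. It names its test, hour, SD and effect, and the arithmetic is right. If 10 msec is taken to hold across the 3 to 5 hour window, as the wording of the objective allows, the rule has 98.9% to 99.9% power over the assumed correlations, so about 99% survives. This stands in part and is why the point is minor. But 9.5 assumes 10 msec only at Tmax, which it places at 3 hours. On that assumption, only the one-hour figure of about 96% is assured.

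A second reply is that 10 msec at one hour with 0 or 5 msec at its neighbours is an artificial profile. That is fair. A gentler 8/10/8 msec profile gives about 96.3% to 98.5% over the same correlations and n, so the lower end of the range does not depend on the sharp drop.

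A third reply is that the restated figures are still a proxy, because the analysis is an MMRM, and that the correlation range is assumed. Both are true and should be said next to the numbers. The restated figures do use the right alpha and the right success rule.

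The last objection runs the other way: the effect is small only at 10 msec. Protocol 4.2 reports maximum mean changes of 7.9 to 11.0 msec in the sponsor's earlier trials, without saying whether they are placebo-corrected. At a true difference of 7.9 msec and n=42, one-hour power would be 75% at 0.05 and 57% at 0.05/3. This limit stands, and the conclusion is therefore tied to the plan's 10 msec.

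**Conclusion.** The concern holds, as a minor inconsistency. The stated power belongs to a test that will not decide assay sensitivity, and no figure is given for the rule that will. At the plan's 10 msec and SD of 5.61 msec, a tested hour has 96.7% (n=42) or 96.3% (n=41) power. The any-of-three rule has about 96% if one hour carries the effect and up to 99.9% if all three do. Against the sized test this is a difference of -2.7 to +0.9 points, so N=42 is not put in doubt on the plan's own effect assumption. The one-hour figures rest only on the plan's inputs and the paired t-test. The range for the rule also rests on the assumed correlations of 0.3 to 0.8 and on how many hours reach 10 msec.

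**What to change.** In Protocol 9.5 and the synopsis, name one-sided alpha 0.05/3 and the any-of-three rule, and replace the 99% statements with text such as:

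> Power is 96.7% (n=42) or 96.3% (n=41) at a tested hour (3, 4 or 5 h) where the moxifloxacin-placebo difference is 10 msec, and about 96% to 99.9% for success at any of the three hours, depending on how many hours reach 10 msec (between-time correlation 0.3 to 0.8 assumed). These figures use a paired t-test with SD 5.61 msec, not the planned MMRM.

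Align the 3-hour Tmax label in 9.5 and the synopsis with the 3 to 5 hour window in the objectives.

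The cost is wording in two places, which can go in with the next protocol amendment. The sample size, design, MMRM and decision rule do not change.

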10. SUPPORTING DOCUMENTATION AND OPERATIONAL CONSIDERATIONS

10.1. Appendix 1: Regulatory, Ethical, and Study Oversight Considerations

10.1.1. Regulatory and Ethical Considerations

This study will be conducted in accordance with the protocol and with the following:

- Consensus ethical principles derived from international guidelines, including the Declaration of Helsinki and CIOMS International Ethical Guidelines;
- Applicable ICH GCP guidelines;
- Applicable laws and regulations, including applicable privacy laws.

The protocol, protocol amendments, ICD, SRSD(s), and other relevant documents (eg, advertisements) must be reviewed and approved by the sponsor, submitted to an IRB/EC by the investigator, and reviewed and approved by the IRB/EC before the study is initiated.

Any amendments to the protocol will require IRB/EC approval before implementation of changes made to the study design, except for changes necessary to eliminate an immediate hazard to study participants.

Protocols and any substantial amendments to the protocol will require health authority approval prior to initiation except for changes necessary to eliminate an immediate hazard to study participants.

The investigator will be responsible for the following:

- Providing written summaries of the status of the study to the IRB/EC annually or more frequently in accordance with the requirements, policies, and procedures established by the IRB/EC;
- Notifying the IRB/EC of SAEs or other significant safety findings as required by IRB/EC procedures;
- Providing oversight of the conduct of the study at the site and adherence to requirements of 21 CFR, ICH GCP guidelines, the IRB/EC, European regulation 536/2014 for clinical studies, European Medical Device Regulation 2017/745 for clinical device research, and all other applicable local regulations.

10.1.1.1. Reporting of Safety Issues and Serious Breaches of the Protocol or ICH GCP

In the event of any prohibition or restriction imposed (ie, clinical hold) by an applicable regulatory authority in any area of the world, or if the investigator is aware of any new information that might influence the evaluation of the benefits and risks of the study intervention, Pfizer should be informed immediately.

In addition, the investigator will inform Pfizer immediately of any urgent safety measures taken by the investigator to protect the study participants against any immediate hazard, and of any serious breaches of this protocol or of the ICH GCP guidelines that the investigator becomes aware of.

